5.5.2 Missing Analysis Values

Unless otherwise specified, missing analysis values will not be imputed for the safety data in this SAP. Specific efficacy missing data imputations are described in the sensitivity analyses in Section 9.1.3. No other standard imputations of missing efficacy data will be applied unless it is described later in the SAP in the respective data section.

5.5.3 Missing or Partial Dates

Adverse Event Start Dates:

- Method 1 Earliest Possible Start Date:
 - o If any combination of the year, month, and/or day are missing then the start date will be set to the earliest possible date that is \geq to the screening date.
- Method 2 Latest Possible Start Date:
 - If any combination of the year, month, and/or day are missing then the start date will be set to the latest possible date that is \leq to the latest possible adverse event end date. If the adverse event is ongoing after the final visit for the subject, then the final visit date will be used.

Prior/Concomitant Medications Start Dates:

- Method 1 Earliest Possible Start Date:
 - o If any combination of the year, month, and/or day are missing then the start date will be set to the earliest possible date that is \geq to the subject's date of birth.
- Method 2 Latest Possible Start Date:
 - o If any combination of the year, month, and/or day are missing then the start date will be set to the latest possible date that is < to the latest possible medication end date. If the medication is ongoing after the final visit for the subject, then the final visit date will be used.

Adverse Event and Prior/Concomitant Medications End Dates:

- Method 1 Earliest Possible End Date:
 - If any combination of the year, month, and/or day are missing then the end date will be set to the earliest possible date that is \geq to the earliest possible adverse event/medication start date.
- Method 2 Latest Possible End Date:
 - o If any combination of the year, month, and/or day are missing then the end date will be set to the latest possible date that is \leq to the subject's final visit date. If the adverse event/medication is ongoing after the final visit for the subject, then the final visit date will be used.

Medical History Disease Onset Dates:

- If year is missing, then the date will not be imputed.
- If both the month and day are missing, then the date will be imputed as July 1st with the year collected. However, if this imputed date is \geq to the screening date then the imputed date will be the screening date minus 1 day.
- If only the day is missing, then the date will be imputed as the 15th with the year and month collected. However, if this imputed date is \geq to the screening date then the imputed date will be the screening date minus 1 day.

5.6 Multiplicity Adjustments and Type I Error

No formal adjustments for multiplicity will be performed for this phase 2 study. All p-values will be tested using alpha at the 0.05 level, two-tailed.

As an exploratory procedure, multiple comparisons for the primary endpoint may be performed, using Hochberg's procedure^[6]. Only the individual NYX-2925 treatment arms versus Placebo would use this method. The Type I error would be set at 0.05. A nested testing procedure is used after the p-values are ranked from largest to smallest. These are the 3 steps that would be followed:

- Step 1: if the largest observed p-value is \leq 0.05, then statistical significance would be declared for all 3 comparisons.
- Step 2: if the largest observed p-value is > 0.05, then the remaining 2 comparisons would be tested against 0.05 / 2 = 0.025. If the second largest observed p-value is ≤ 0.025 , then statistical significance would be declared for the 2 smallest p-value comparisons.
- Step 3: if the second largest observed p-value is > 0.025, then the last comparison would be tested against 0.05 / 3 = 0.017. If the smallest observed p-value is ≤ 0.017 , then statistical significance would be declared only for the smallest p-value comparison.

5.7 By-Center Analyses

The study includes 39 study sites in the United States. Some study sites will not have all four treatment arms assigned to randomized subjects. Only the primary efficacy data described in Section 9.1 will be summarized using descriptive statistics by study site. No other by-center analyses will be planned in this SAP. Study site will not be included as a covariate in any statistical models.

6.1 Safety Population

All subjects who were dispensed study drug during the baseline visit and did not return all the study drug in their next visit will be in the safety population. It will be assumed that these subjects in the

safety population have taken at least one dose of study drug. Study drug is not referring to rescue medication that was dispensed at screening or at any other visits.

Subjects in the safety population will be used for all analyses of safety data and will be analyzed based on the actual treatment received in the study. In the event subjects received study drug with multiple study drug treatments by mistake in the study, the following analyses will be updated:

- Latest Treatment and Lowest NYX-2925 Dose Given:
 - o If 10 mg was the lowest NYX-2925 dose given, then that will be used for the remainder of the study after that study drug has been dispensed.
 - o If 50 mg was the lowest NYX-2925 dose given, then that will be used for the remainder of the study after that study drug has been dispensed.
 - o If 200 mg or placebo was given, then NYX-2925 200 mg will be used for the remainder of the study after that study drug has been dispensed.
 - This method will be applied to data regarding: adverse events, concomitant medications, study drug accountability, study drug exposure, and rescue medication.
 - o For example, if a subject received placebo for weeks 1-2 and then received a kit for NYX-2925 50 mg, then 2 different safety treatment arms would be assigned for this subject. Safety data mentioned above in weeks 1-2 would be counted in the placebo group and any time after receiving NYX-2925 50 mg will be counted in the NYX-2925 50 mg group.
- Lowest NYX-2925 Treatment:
 - o Placebo will not be used.
 - Each subject will only be counted in one NYX-2925 treatment group (10 mg, 50 mg, or 200 mg).
 - This method will be applied to all safety data not mentioned above (i.e. clinical laboratory tests, vital sign measurements, electrocardiogram, physical examinations, etc.).

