12.4 Analysis Populations

Safety analyses will be based on the Safety Population, which is defined as all subjects who receive at least 1 dose of investigational product.

Efficacy analyses will be based on the modified Intent-to-Treat Population, which is defined as all subjects in the Safety Population with at least 1 post baseline assessment of the pain intensity NRS.

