4.1 Study Drug Treatment Arms

Subjects will be dispensed blinded investigational product according to the randomization schedule. Investigational product will be dispensed at the Week 0 (Baseline) and Week 2 visits; at each of the 2 visits, subjects will receive a 2-week supply of investigational product. All capsules are identical in appearance and the strengths are placebo, 10 mg, 50 mg, and 100 mg.

- 10 mg of NYX-2925 by mouth once daily for 4 weeks
- 50 mg of NYX-2925 by mouth once daily for 4 weeks
- 200 mg of NYX-2925 by mouth once daily for 4 weeks
- Placebo by mouth once daily for 4 weeks

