6.2 Efficacy Population

The efficacy population will be based on subjects included in the safety population, were randomized, and have at least 4 post-baseline daily scores for the NRS assessment score assessing average pain intensity in the past 24 hours or at least one post-baseline visit (Week 2, Week 4, or Early Termination).

Subjects will be excluded from the efficacy population in the event a subject is given study drug by mistake without being randomized. This will also be classified as a major protocol violation.

Subjects in the efficacy population will be analyzed based on the planned treatment they were randomized to in the study. The efficacy population will be the primary analysis population used for this study.

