6.3 PP Population

The Per Protocol (PP) population will be based on all subjects in the efficacy population and the following criteria:

- Subjects received the same study drug throughout the duration of the study;
- Subjects received the same study drug to which they were randomized;
- Subjects met the randomization inclusion criteria described in Section 7.1 of the protocol;
- Subjects did not use any of the prohibited concomitant medications listed in Section 8.7 of the protocol;
- Subjects who have an overall study drug treatment compliance between 80% and 125%;
- Subjects have an observed mean NRS score assessing average pain intensity in the past 24 hours calculated within the Week 4 efficacy analysis visit window.

Subjects in the PP population will be defined based on a review of the relevant data by the Sponsor prior to database lock. However, subjects dispensed the wrong treatment arm (i.e., a treatment arm other than the one they were randomized to) will be removed from the PP population. Subjects in the PP population will be analyzed based on the planned treatment they were randomized to in the study.

7. Disposition, Baseline, and Other Characteristics

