8.1 Study Drug Accountability

Subjects will be dispensed blinded study drug according to the randomization schedule at visits Week 0 (Baseline) and Week 2. In the event the subject comes in for an unscheduled visit prior to Week 4, they may be dispensed additional blinded study drug.

The following data will be collected and derived at each start and end to the study drug accountability visit intervals:

Parameter	Origin/Derivation
Capsules Dispensed Amount	CRF
Capsules Returned Amount	CRF
Expected Number of Capsules Taken	Derived: (Date Returned – Date Dispensed + 1) x 2 (where the maximum would be 36 because 36 capsules are issued at each dispensing visit)
Estimated Number of Capsules Taken	Derived: Number of Capsules Dispensed Amount – Number of Capsules Returned Amount
Treatment Compliance (%)	Derived: 100 x Estimated Number of Capsules Taken / Expected Number of Capsules Taken (rounded off by one number after the decimal point)

The Overall Treatment Compliance (%) will be calculated as:

• 100 x \sum (Estimated Number of Capsules Taken at All Visits) $/\sum$ (Expected Number of Capsules Taken at All Visits) and rounded off by one number after the decimal point

A subject will be classified as being compliant with study drug administration if their calculated compliance by analysis visit and overall is between 80% and 125%, inclusive. Descriptive statistics will be summarized for treatment compliance by returning analysis visits Week 2, Week 4, and Overall. The following categorical ranges will be summarized in a table for those same analysis visits and overall:

• <80%, 80-125%, >125%, and Not Reported

Any study drug not returned during a subject's visit where study drug compliance is assessed will assume that all of that study drug was taken by the subject for analysis purposes. No adjustments will be made even if comments are documented on the CRF that stated lost samples were reported by the subjects. All study drug accountability comments will be provided in a subject listing. If a subject does not return study drug after being dispensed study drug, then the study drug returned and overall treatment compliance will be set to missing.

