8.2 Study Drug Exposure

The study will be packaged in a way that each dose will be 2 capsules/row, with the following blinded configuration for each treatment arm:

Due to the nature of this study and data collection, it will be assumed each capsule taken by the subjects will have equal treatment weight for study drug compliance and exposure. After database lock and when the study drug treatment is unblinded, each kit number assigned to a subject will be

verified that correct treatment arm was given based on the randomization schedule. Any incorrect treatment arm kit given where the estimated number of capsules taken defined in Section 8.1 is greater than zero, will be defined as a major protocol deviation. Study drug exposure will be listed and summarized based on the treatment arm subjects received. Any combinations of different treatment arms may be identified (i.e. receiving 50 mg of NYX-2925 dose for kit and receiving 200 mg of NYX-2925 dose for another kit).

The number of study days of study drug exposure will be summarized using descriptive statistics based on the date of the last dose of study drug collected in the subject disposition CRF page. If the last dose of study drug was not collected in the subject disposition CRF page, the last date of study drug returned will be used as the estimated date. If a subject does not return study drug after being dispensed study drug and the date of the last dose of study drug was not collected, then the number of study days will be set to missing.

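### The SAP's Safety Population rule looks only at the baseline supply, so a subject who returns all of it and is dosed from a later supply falls out of the safety tables and the primary analysis

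*SAP*

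**What the plan says.** Protocol 12.4 ties the population to dosing: "Safety analyses will be based on the Safety Population, which is defined as all subjects who receive at least 1 dose of investigational product".

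SAP 6.1 replaces this with an accountability rule, "All subjects who were dispensed study drug during the baseline visit and did not return all the study drug in their next visit", and assumes that those subjects took at least one dose. SAP 5.1.1 gives the reason for a proxy: subjects dose themselves and the CRF does not record the first dosing date.

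Drug is issued more than once. SAP 4.1: "Investigational product will be dispensed at the Week 0 (Baseline) and Week 2 visits". SAP 8.1: "In the event the subject comes in for an unscheduled visit prior to Week 4, they may be dispensed additional blinded study drug". SAP 8.1 puts each dispensing at 36 capsules, and protocol 8.2 puts a kit at 18.

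The other populations are built on this one. SAP 6.2: "The efficacy population will be based on subjects included in the safety population, were randomized", with a further condition on post-baseline diary scores or visits. SAP 6.3: "The Per Protocol (PP) population will be based on all subjects in the efficacy population". SAP 6.2 makes the Efficacy Population the primary analysis population.

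SAP 4.7 lists changes from the protocol. It records that the Efficacy Population replaces the modified intent-to-treat population. It has no entry for the Safety Population.

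**The concern.** With no first-dose date, inferring dosing from capsule counts is reasonable. Inferring it from the first dispensing interval alone is not, when the schedule has a second dispensing and allows unscheduled ones. The rule can classify a dosed subject as undosed.

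Two things are at stake. The subject's adverse events, laboratory values and ECGs would be missing from the safety tables. And a randomized subject who may have a complete Week 4 diary would be dropped from the primary comparison because of something that happened to the drug supply after randomization.

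**Working it through.** This is a question of logic, so there is no stated figure to reproduce. The check applies each rule in turn to one subject and then asks which losses the rule itself causes.

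**1. The subject.** Baseline supply of 36 capsules, all 36 returned at the next visit; a later supply is issued and at least one dose is taken from it.

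**2. Safety.** Capsules taken in the first interval (SAP 8.1: dispensed minus returned) = 36 − 36 = 0, so SAP 6.1 is not met. Capsules taken from the later supply exceed 0, so protocol 12.4 is met. The two documents classify the subject differently.

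**3. Efficacy.** SAP 6.2 requires Safety membership, so the subject is out, even with enough diary scores or a post-baseline visit.

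**4. Per protocol.** SAP 6.3 requires Efficacy membership, so the subject is out here too. SAP 6.3 also requires overall compliance of 80% to 125%, so the question is whether the subject would have qualified anyway. Assume the whole supply is returned and replaced on Day r, visits fall on Days 14 and 28, and dosing is daily to Day 28. SAP 8.1 sets expected capsules per interval at 2 × (days, counting both ends), with a maximum of 36.

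- For r < 14: expected = 2r + 2(14 − r + 1) + 2(28 − 14 + 1) = 60.
- For r = 14: expected = 28 + 30 = 58.
- Taken = 2(28 − r + 1) if dosing starts on Day r, or 2(28 − r) if it starts the day after.

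| Replacement day r | Expected | Taken, starting Day r | Compliance | Compliance, starting the day after |
|---|---|---|---|---|
| 2 | 60 | 54 | 90.0% | 86.7% |
| 3 | 60 | 52 | 86.7% | 83.3% |
| 4 | 60 | 50 | 83.3% | 80.0% |
| 5 | 60 | 48 | 80.0% | 76.7% |
| 6 | 60 | 46 | 76.7% | 73.3% |
| 14 | 58 | 30 | 51.7% | 48.3% |

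So SAP 6.1 is the cause of a per-protocol loss only for a replacement by about Day 4 or 5. A Week 2 starter fails the compliance limit regardless.

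**5. Size.** One subject in an arm of 75 is 1/75 = 1.3%. The documents give no count. Assuming 0 to 3 such subjects, the loss is 0 to 3/300 = 1.0% of the trial, or at most 3/75 = 4.0% of an arm if all fell in the same one.

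**The case against.** The strongest reply is that SAP 6.1 tries to put the protocol's definition into practice without a first-dose date, and that the gap is an edge case. No section describes exchanging a fully returned supply, and the unscheduled dispensing in SAP 8.1 reads more like a top-up. The schedule of procedures places drug return at Visits 3 and 4. If the next visit in SAP 6.1 means the next scheduled one, a subject whose supply was exchanged on Day 3 and who used the replacement has not returned everything by Week 2, and is included.

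Much of this stands. The early-exchange case, and with it the per-protocol loss, depends on reading the next visit to include unscheduled ones. The Week 2 case does not: a subject who takes nothing for two weeks, returns the full supply at Week 2 and then starts the scheduled second supply fails the rule on either reading. No other section restores that subject.

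A reader might infer more than the documents support:

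- *That one unused kit excludes a subject.* It does not; all 36 capsules must come back, and a kit holds 18.
- *That the SAP foresees kit exchanges.* SAP 8.2 treats as a major deviation "Any incorrect treatment arm kit given where the estimated number of capsules taken defined in Section 8.1 is greater than zero", which allows for kits issued but not used. But that check is made after database lock and unblinding, so it cannot prompt an exchange during the trial.
- *That subjects first supplied after baseline are also lost.* The literal rule would miss them, but protocol 10.2 places randomization and dispensing at Visit 2, and no later route is described.
- *That the data disappear.* SAP section 14 lists all subjects whatever their randomized or treated status, and SAP section 6 reports reasons for exclusion. The data are missing from the safety tables, not from the report.

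**Conclusion.** The point holds in a limited form. As written, SAP 6.1 misclassifies a subject who returns the whole baseline supply at the next visit and is then dosed from the Week 2 or an unscheduled supply. The subject is left out of the Safety Population and, by nesting, out of the primary analysis, contrary to protocol 12.4 and without an entry in SAP 4.7.

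The number affected is probably small and may be zero; the 0-to-3 range is an assumption. At about 1.3% of an arm per subject, no effect on the trial's conclusions is shown or claimed. It would be wrong to read this as a general per-protocol problem, because after a Week 2 replacement the 80% limit excludes the subject anyway. The correction is still worth making: the rule gives a wrong answer for a case that the dispensing schedule permits, and settling it before database lock avoids deciding after unblinding whether a dosed subject counts.

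**What to change.** - **SAP 6.1.** Define the Safety Population as subjects whose estimated capsules taken (SAP 8.1, dispensed minus returned) exceed zero in any dispensing interval, or who have a last-dose date on the disposition CRF. State that unreturned drug counts as taken for this purpose. SAP 8.1 sets the returned amount to missing when nothing comes back, and those subjects must not drop out.
- **SAP 5.1.1 and 10.1.** SAP 5.1.1 assumes that the first dose falls on Day 1, and SAP 10.1 counts treatment-emergent events from the baseline visit and dispensing. For subjects whose whole baseline supply was returned, take the first-dose date and the start of the treatment-emergent period from the first dispensing with capsules taken. Otherwise a Week 2 starter's pre-dose events would count as treatment-emergent. Keep Day 1 itself at Visit 2 so that the diary weeks do not move.
- **SAP 4.7.** List any remaining difference from protocol 12.4.

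The cost is short edits in four sections and a little extra derivation for a few subjects at most. The accountability counts and last-dose date are already on the CRF.

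### For subjects dispensed more than one treatment, SAP 6.1 tabulates labs, vital signs and ECG under the lowest NYX-2925 dose whatever was being taken, and its adverse-event rule is inconsistent

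*SAP*

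**What the plan says.** SAP 6.1 states that safety subjects "will be analyzed based on the actual treatment received in the study". It then sets two special rules: "In the event subjects received study drug with multiple study drug treatments by mistake in the study".

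The first rule is headed with both the latest treatment and the lowest NYX-2925 dose given. Its bullets read "If 10 mg was the lowest NYX-2925 dose given, then that will be used for the remainder of the study", then "If 50 mg was the lowest NYX-2925 dose given, then that will be used for the remainder of the study", then "If 200 mg or placebo was given, then NYX-2925 200 mg will be used for the remainder of the study". Each is qualified as running from the point when that drug was dispensed. Its scope is stated: "This method will be applied to data regarding: adverse events, concomitant medications, study drug accountability, study drug exposure, and rescue medication". The worked example is a subject on placebo in Weeks 1-2 and then 50 mg. Data from the first two weeks stay under placebo and later data go under 50 mg.

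The second rule covers all remaining safety data, including labs, vital signs, ECG and physical examinations. It rules out placebo as a label and adds: "Each subject will only be counted in one NYX-2925 treatment group (10 mg, 50 mg, or 200 mg". That group is the lowest NYX-2925 dose, with no reference to time.

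SAP 8.2 treats mixed dispensing as a practical possibility. Its example is "receiving 50 mg of NYX-2925 dose for kit and receiving 200 mg of NYX-2925 dose for another kit".

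**The concern.** Both rules can report a result under a treatment the subject was not taking when it arose, which conflicts with the actual-treatment principle stated just before them. Between two active doses, any relabelling goes one way, to the lower dose.

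Safety and tolerability of multiple dose levels is a secondary objective (SAP 3.2). The outputs exposed are those where one subject can matter: the adverse-event summaries, the potentially clinically significant lab table, the QTcF table and the eDISH plots. SAP 13 marks the overall adverse-event, potentially clinically significant lab, QTcF and eDISH outputs for topline delivery. A rare finding on 200 mg could appear at 10 mg, or an on-placebo finding under active drug.

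The adverse-event text also supports two readings, so two programmers could produce different tables from it.

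**Working it through.** No stated figure is at issue, so the check applies the rules to every case.

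**Inputs.** There are four treatments (placebo, 10, 50 and 200 mg) and two scheduled dispensings, Week 0 and Week 2 (SAP 4.1). Liver tests and vital signs are taken at Week 2. Full labs, vital signs, ECG and brief physical examination are taken at Week 4 or early termination (SAP Appendix I). There are about 75 subjects per arm (SAP 4.3). A kit holds 18 capsules (Protocol 8.2) and 36 capsules are issued per dispensing visit (SAP 8.1), so 36 / 18 = 2 kits per dispensing.

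**Enumeration.** With one treatment per dispensing and a different one at each, there are 4 x 3 = 12 ordered sequences. The table counts those in which the reporting label differs from the drug dispensed for the period. The first rule is read literally, with placebo time before any active drug left under placebo as in the SAP's example.

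| Sequence type | Sequences | First rule: adverse events mislabelled | Second rule: Week 2 data mislabelled | Second rule: Week 4 data mislabelled |
|---|---|---|---|---|
| Placebo then active | 3 | 0 | 3 | 0 |
| Higher then lower active dose | 3 | 0 | 3 | 0 |
| Lower then higher active dose | 3 | 3 | 0 | 3 |
| Active then placebo | 3 | 3 | 0 | 3 |
| Total | 12 | 6 | 6 | 6 |

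Under the second rule each sequence is mislabelled at exactly one of the two visits, so all 12 are affected somewhere. Labelling each period by what was dispensed for it gives 0 of 12.

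**Examples under the second rule.**
- 200 then 10 mg: Week 2 liver tests, after 200 mg only, go under 10 mg.
- 10 then 200 mg: Week 4 labs and ECG, on 200 mg, go under 10 mg.
- Placebo then 200 mg: Week 2 liver tests, after placebo only, go under 200 mg.

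**ECG alone.** The only scheduled post-baseline ECG is at Week 4 or early termination, so the Week 4 column applies: 6 of 12.

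**First rule, two readings.** Read literally, 10 then 200 mg makes 10 mg the lowest dose given, and it governs the rest of the study. If instead the latest dispensing governs, as the heading and example suggest, the lowest-dose wording matters only when strengths are mixed within one dispensing. Two kits per dispensing make that possible: 10 with 200 mg becomes 10 mg, and 50 with 200 mg becomes 50 mg. The third bullet, taken alone, would label placebo time as 200 mg, which does not fit the SAP's example.

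**Size.** Take one subject randomised to 200 mg, given 10 mg at Week 2, with ALT above 3 x ULN at Week 2.
- Second rule: 10 mg 1/76 = 1.3%; 200 mg 0/74 = 0%.
- By treatment taken: 200 mg 1/75 = 1.3%; no event under 10 mg.

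If the subject has no event, only denominators change. With an assumed five events in the arm left, 5/75 = 6.67% becomes 5/74 = 6.76%, about 0.1 point. The documents give no mis-dispensing count. Assuming 1, 2 or 5 such subjects in an arm, all with the event, gives 1/75 = 1.3, 2/75 = 2.7 or 5/75 = 6.7 points.

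**The case against.** **Traceability.** The rules apply only to mistakes, and an interactive response system controls dispensing (Protocol 8.3). Kits are checked after unblinding and wrong-arm kits are major deviations (SAP 8.2). These subjects are listed (SAP 14, listing 16.2.2.2), non-efficacy listings are by actual arm (SAP 5.2), and safety is descriptive (SAP 5.3.4). All of this stands and limits the harm, but it does not correct the summary tables or eDISH plots.

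**Excluding placebo as a label.** This keeps anyone exposed to active drug out of the comparator. Protocol 6.3 also argues from rat data that analgesic effects outlast the drug, so calling placebo time after active drug active is not plainly wrong. That part stands as a possible convention. It cannot justify placing results obtained before any active dose under active drug.

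**Pooled column.** Swaps between active doses leave the column for all NYX-2925 doses unchanged. This is true, but the objective is by dose level, and the placebo relabelling does alter that column.

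**Stronger readings the documents do not support.**
- A reader might infer that adverse events on 200 mg are always moved to a lower dose. Events on 200 mg before a later 10 or 50 mg kit stay under 200 mg even on the literal reading. On the period-based reading only mixed kits are affected.
- A reader might infer that each misassigned subject shifts a rate by 1.3 points. That requires the subject to have the event.
- A reader might infer that ECG is mislabelled in every sequence. At the scheduled visit it is confined to lower-then-higher and active-then-placebo.
- A reader might infer that a 200 mg signal will be hidden. With no mis-dispensing count given, the effect could be nil.

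**Conclusion.** The concern holds in a bounded form. For labs, vital signs, ECG and physical examinations, the second rule of SAP 6.1 contradicts the actual-treatment principle, and no reading or other section removes the conflict. For adverse events, the bullets, heading and example do not agree. The outcome depends on the reading: 6 of 12 sequences mislabelled if literal, mixed kits only if period-based.

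The size is about 1.3 percentage points per affected subject with an event. For one without, it is about 0.1 point in the five-event illustration. Both figures assume about 75 per arm and the assumed numbers shown above. Efficacy is untouched, because it is analysed by randomised treatment (SAP 6.2). The point should be corrected because the text is wrong on its own terms and rare-event outputs can turn on one subject.

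**What to change.** Replace both rules in SAP 6.1 with one period-based reporting rule, fixed before unblinding:

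- Assign each adverse event to the treatment dispensed for the period in which it started.
- Assign each visit's labs, vital signs, ECG and examinations to the treatment dispensed for the interval before that visit. Placebo-only intervals then stay under placebo.
- Carry the same assignment into worst-value, any-post-baseline and eDISH outputs, so that one value never appears in two arms.
- Count denominators by treatment actually taken.
- For different strengths mixed within one dispensing, dates cannot separate the kits. State one convention, for example the highest strength taken, and use it for adverse events, by-visit data and whole-study outputs alike.
- Footnote these subjects in the affected tables.

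The cost is SAP wording and derivation code, since SAP 8.2 already verifies treatment by kit. The drawback is that a mis-dispensed subject may appear in more than one column, which the SAP's own adverse-event example already accepts.
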